8.4.11. Zarit Caregiver Burden Inventory

All Part 1 safety analyses will be performed for the Safety population (SAF), as defined in Section 6.2. Results will be reported by treatment group for the 16-week treatment period, unless noted otherwise.

9.1. EXTENT OF EXPOSURE

Part 1 treatment exposure data will be summed.

Duration of total exposure.

Duration of total exposure during Part 1 (i.e., time on treatment (in days)) will be calculated per subject as the number of days with IMP intake during the trial and will be summarized using n, mean, standard error, median, minimum, Q_1 , Q_3 and maximum.

This will be calculated for non-placebo subjects as:

Date of last IMP intake in Part 1 - Date of first full daily IMP intake in Part 1 + 1 Time on treatment will be summarized by the Part 1 treatment group.

TREATMENT COMPLIANCE (DIARY) 9.2.

Study medication is to be administered twice daily, and self-reported compliance is recorded in the eDiary as full (both doses), partial (less than full daily dose) or missed (both doses) each day. From this, compliance will be calculated by assuming that a missed dose=0% of dose consumed, partial=50% of dose consumed, and full=100% of dose consumed. For each subject, a daily diary compliance score will be thus obtained.

A compliance will also be determined based on the actual quantity taken, determined using the weight of the dispensed drug kit and weight of the returned drug kit. The expected quantity taken will be determined using the assigned dosage in mg/kg/day and the number of days they were assigned at that dosage. If a kit was not returned, the compliance for the period will be missing.

For Part 1, compliance will be summarized for the SAF and mITT populations over the course of T+M period and M period only per recorded visit dates, reported by treatment group.

9.3. **ADVERSE EVENTS**

An AE is defined as any unfavorable and unintended sign (including an abnormal, clinically significant laboratory finding), symptom, or disease temporally associated with the use of a medicinal (investigational) product, whether or not considered related to the medicinal (investigational) product. For Part 1, the period of observation for adverse events extends from the time the subject gives informed consent until the end of the titration/transition period (Visit 13 or 15).

A treatment-emergent adverse event (TEAE) in Part 1 is defined as any AE that based on start date information occurs after the first intake of study treatment in Part 1, but not on or after the first dose of study treatment in Part 2. For subjects who participate in Part 2, the Part 1 TEAE will include events with onset up to the day prior to the date of first dosing in Part 2. A Part 1 TEAE will be further classified into the Titration Period, Maintenance Period, and Transition/Taper Period. The Titration Period will include all events with onset from the date of the Visit 6. The Maintenance period will include all events with onset from the day after Visit 6 through the date of Visit 12. The Transition/Taper period will include all events with onset starting with the day after Visit 12 through Visit 15.

For Part 1, tables will present TEAE data by assigned treatment group received in Part 1. AEs occurring after enrollment and prior to the first administration of study treatment in Part 1 are defined as non-treatment emergent AEs (non-TEAEs).

AEs are categorized as related or unrelated. If the AE is thought to be definitely, probably or possibly related to study drug then it is to be categorized as related. Possibly or definitely unrelated is categorized as unrelated. Any TEAE with missing relationship will be considered as "related."

The severity of AEs (for both nonserious and serious AEs) will be assessed by the investigator as follows:

Severity Definition of Adverse Events:

Mild - A type of AE that is usually transient and may require only minimal treatment or therapeutic intervention. The event does not generally interfere with usual activities of daily living.

Moderate - A type of AE that is usually alleviated with additional specific therapeutic intervention. The event interferes with usual activities of daily living, causing discomfort but poses no significant or permanent risk of harm to the research participant.

Severe - A type of AE that interrupts usual activities of daily living, or significantly affects clinical status, or may require intensive therapeutic intervention.

Any AE with missing severity will be imputed as "severe."

The original terms used by the investigators in the eCRFs to identify AEs will be coded using the MedDRA Version 20.1 or later.

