Part 1 consists of a 4-week baseline, 2-week titration, 12-week maintenance, and 2week taper or transition period. The 4-week Baseline Period consists of the establishment of initial eligibility during a screening visit to include an assessment of cardiac parameters (ECG and ECHO), followed by an observation period where subjects will be assessed for baseline seizure frequency based on recordings of daily seizure activity entered into a diary. Upon completion of the Baseline Period, subjects who qualify for the study are randomized (1:1:1) in a double-blind manner to receive 1 of 2 doses of ZX008 (0.2 mg/kg/day, 0.8 mg/kg/day; maximum dose: 30 mg/day [or 0.5] mg/kg/day, maximum 20 mg/day, for subjects taking concomitant STP]) or placebo. Randomization is stratified by weight (<37.5 kg, $\ge 37.5 \text{ kg}$) to ensure balance across treatment arms, and at least 25% of subjects will be in each weight group. All subjects are titrated to their blinded randomized dose over a 2-week Titration Period. Following titration, subjects continue treatment at their randomly assigned dose over a 12-week Maintenance Period. Total treatment time from the beginning of the Titration Period through the end of the Maintenance Period is 14 weeks. Subjects will have ECG and ECHO assessments at weeks 6 and 14 during the Maintenance Period. At the end of the Maintenance Period (or early discontinuation), all subjects undergo a blinded 2-week taper or transition period (Post-Dosing Follow-Up) depending on whether they exit the study or are enrolled in Part 2, the long-term open-label extension, respectively. Cardiac safety follow-up visits are performed after study drug discontinuation for early termination, or for those subjects who complete the study but do not enter the openlabel extension part. All subjects are required to have follow-ups at 3 and 6 months. Subjects enrolled in Germany, France and Netherlands will have an additional follow-up at 24 months. If there are any findings at a post-dose follow-up, a follow-up visit will be scheduled every 3 months until resolved or stabilized.

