4.3. TREATMENT ASSIGNMENT & BLINDING

Upon completion of the Baseline Period in Part 1, subjects who qualified for the study were randomized (1:1:1) in a double-blind manner to receive 1 of 2 doses of ZX008 (0.2 mg/kg/day, 0.8 mg/kg/day; 30mg/day maximum [0.2 mg/kg/day or 0.5 mg/kg/day; 20 mg/day maximum for subjects taking concomitant STP]) or placebo. The randomization was stratified by weight (<37.5 kg, $\ge37.5 \text{ kg}$) to ensure balance across treatment arms, with a target of at least 25% in each weight group. Subjects were assigned a randomization number by the IWR system upon confirmation that the subject qualified for enrollment in the Titration Period.

The primary biostatistical team, data management team, and clinical team will remain blinded to subject treatment assignments until approval is given for the unblinding of the Part 1, Cohort A database and finalization of inclusion in the study populations is made.

The release of unblinded pharmacokinetic concentration data, ECG and ECHO data to facilitate external analyses will be completed only after the approval for unblinding of the Part 1 database by Zogenix.

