6.3. MODIFIED INTENT-TO-TREAT (MITT) POPULATION

Salthoril Ation The mITT Population is defined as all randomized subjects who receive at least one dose of ZX008 or placebo and for whom at least one week of diary data are available. Subjects will be analyzed according to the treatment group to which they were randomized. The primary comparison of ZX008 0.8 mg/kg/day to placebo, as well as key secondary analyses, will be performed on the mITT Population.

PER PROTOCOL (PP) POPULATION 6.4.

The PP Population is defined as all randomized subjects who receive at least one dose of ZX008 or placebo, who complete at least 4 weeks of diary data in the maintenance period, and who have no major protocol deviations that would have a significant impact on clinical outcome of Part 1 data, and who have met the inclusion criteria for baseline drop seizure count. Protocol deviations that occurred during Part 1 will be reviewed and the list of deviations warranting exclusion from the PP Population will be finalized prior to study unblinding.

PROTOCOL DEVIATIONS 6.5.

Major protocol deviations will be summarized overall and by site based on the SAF population. Major protocol deviations are those that have the potential to impact subject safety and/or affect data integrity and/or the efficacy conclusions. Major protocol deviations will be grouped into categories and may include categories such as:

- Violation of inclusion/exclusion criteria
- Violation of randomization inclusion criteria
- Non-compliance regarding intake of IMP
- Inappropriate intake of concomitant medication
- Subject not discontinued as per protocol
- Other non-compliance

Multiple deviations can occur in the same subject and thus a subject can be counted in more than 1 deviation category.

Major and minor protocol deviations will be presented in a subject data listing for the enrolled population, sorted by treatment, site, subject, and study part.

Deviations will be reviewed prior to the database lock of Part 1 data to determine which deviations will be classified as leading to exclusion from the PP set.

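### Bottle-weight compliance in Section 9.2 omits the daily dose maximum, so as written it understates adherence for heavier subjects in the 0.8 mg/kg/day arm

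*SAP*

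**What the plan says.** Section 9.2 gives two compliance measures. The first is scored from the diary (full, partial or missed dose each day). The second compares actual with expected quantity. The actual quantity is "determined using the weight of the dispensed drug kit and weight of the returned drug kit". For the expected quantity the rule is: "The expected quantity taken will be determined using the assigned dosage in mg/kg/day", combined with the days spent at that dosage. Both measures are summarised by treatment group for T+M and for M, in the SAF and mITT populations.

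The dose itself is defined elsewhere with a ceiling. Section 4 gives "0.8 mg/kg/day; maximum dose: 30 mg/day", and Section 4.3 gives "0.5 mg/kg/day; 20 mg/day maximum for subjects taking concomitant STP". Section 4.4 adds that the IWR system tells the site what volume to give on the basis of body weight, and that the dose is recalculated once at the midpoint of Part 1.

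Section 14 indexes separate bottle-weight tables for the mITT Population (14.1.5.2.3.x). The SAP addendum lists further ones for the Safety Population (14.1.5.2.4.x).

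**The concern.** The two halves of the ratio rest on different doses. The numerator comes from kit weights, so it reflects the capped amount that was given. The denominator, as worded, is the uncapped mg/kg/day figure. For anyone whose weight-based dose exceeds the ceiling, taking every dose yields a score below 100%.

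The error is not spread evenly. It falls almost entirely on the 0.8 arm, and within that arm on the heavier subjects. That group is not rare: "Randomization is stratified by weight (<37.5 kg", with 37.5 kg and above as the other stratum, and "at least 25% of subjects will be in each weight group". The bottle-weight table is read by comparing arms. A reader would see lower adherence on the high dose and could take it for a tolerability or acceptability problem, when the formula alone produced it.

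**Working it through.** **Inputs, all from the SAP**
- High dose 0.8 mg/kg/day, maximum 30 mg/day (Section 4).
- With STP: 0.5 mg/kg/day, maximum 20 mg/day (Sections 4 and 4.3).
- Low dose 0.2 mg/kg/day, with the same maxima (Section 4.3).
- Titration in the 0.8 arm: days 1–4 at 0.2, days 5–8 at 0.4, days 9–14 at 0.8 mg/kg/day (Table 1), then 12 weeks (84 days) of maintenance.
- Weight stratum boundary 37.5 kg (Section 4).

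The SAP states no expected compliance figure, so there is none to reproduce.

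**Step 1. Weight at which the maximum binds** = maximum ÷ dose.
- 0.8 arm: 30/0.8 = 37.5 kg, which coincides with the stratum boundary. The SAP does not say that the boundary was derived this way.
- 0.8 arm with STP: 20/0.5 = 40 kg.
- 0.2 arm: 30/0.2 = 150 kg; with STP 20/0.2 = 100 kg.

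**Step 2. Score of a fully adherent subject, Maintenance Period** = min(dose × weight, maximum) ÷ (dose × weight). Above the binding weight this is 37.5/weight, or 40/weight with STP.

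| Weight | 0.8 mg/kg/day | With STP |
|---|---|---|
| 40 kg | 30/32 = 93.8% | 20/20 = 100% |
| 50 kg | 30/40 = 75.0% | 20/25 = 80.0% |
| 60 kg | 30/48 = 62.5% | 20/30 = 66.7% |
| 75 kg | 30/60 = 50.0% | 20/37.5 = 53.3% |

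**Step 3. The same over T+M (0.8 arm, no STP, constant weight).** The uncapped total is 4 × 0.2 + 4 × 0.4 + 90 × 0.8 = 74.4 mg/kg.
- 50 kg: allowed 40 + 80 + 90 × 30 = 2,820 mg; formula 74.4 × 50 = 3,720 mg; score 75.8%.
- 60 kg: allowed 48 + 96 + 2,700 = 2,844 mg; formula 4,464 mg; score 63.7%.
- 40 kg: allowed 32 + 64 + 2,700 = 2,796 mg; formula 2,976 mg; score 94.0%.

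Titration softens the shortfall by about one percentage point or less at these weights.

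**Step 4. Effect on the arm mean (illustration).** The SAP gives no weight distribution. Its floor of 25% per stratum leaves a share of 25% to 75% in the heavier stratum. Suppose everyone there weighs 50 kg, nobody takes STP, the arm has the same split as the study, and adherence is perfect. The 0.8-arm mean in M would then be 0.75 × 100 + 0.25 × 75 = 93.8% at the low end of the share and 0.25 × 100 + 0.75 × 75 = 81.3% at the high end. The 0.2 arm would score 100%. The single weight of 50 kg is an assumption, not a figure from the SAP.

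**Step 5. Check of the correction.** With min(dose × weight, maximum) in the denominator as well, a fully adherent subject scores 100% at every weight.

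**The case against.** The strongest reply is that Section 9.2 omits the maximum but does not rule it out. The sentence is not a complete formula: mg/kg/day times days gives mg/kg, so body weight and concentration must come from elsewhere, and placebo has no mg/kg/day dosage at all. A programmer could reasonably read the assigned dosage as the capped dose of Sections 4 and 4.3. That reading is possible. It is not what the sentence says, however: it names the unit mg/kg/day, the ceiling is in mg/day, and Section 4.4 and Table 1 label the arms by the uncapped figures. The incompleteness is itself a reason to rewrite the sentence.

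The diary measure is unaffected and has its own tables, so a deficit seen only by bottle weight would be visible as a discrepancy. That stands and limits the harm.

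A reader might infer two stronger conclusions, and the document supports neither.
- *That nearly all heavier high-dose subjects would be classed as non-compliant.* The SAP sets no cut-off and classifies nobody from this measure. Even under an assumed 80% cut-off, everyone from 37.5 up to 37.5/0.8 = 46.9 kg would pass. The share of those above 37.5 kg who fail would run from 49% to 87% across assumed normal weight distributions (mean/SD from 45/8 to 60/15 kg).
- *That compliant high-dose subjects would be selectively removed from the per-protocol set.* Section 6.5 does name "Non-compliance regarding intake of IMP" as a possible major-deviation category, but with no percentage and no reference to kit weights. Sections 4.3, 6.4 and 10 have populations and exclusions settled before unblinding, and Section 4.4 blinds staff to allocation and concentration. The people deciding exclusions should therefore not hold this arm-specific figure.

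**Conclusion.** The point holds as a conflict between Section 9.2 and the SAP's own dose definition. Taken as written, the rule scores a fully adherent 0.8-arm subject at 37.5/weight above 37.5 kg, or 40/weight above 40 kg with STP, and leaves the 0.2 arm essentially untouched. The result is a one-arm distortion in a planned by-treatment table. Its size for an individual is fixed by weight; its size for the arm depends on a weight distribution that the SAP does not give.

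This rests on a literal reading of the denominator, on constant weight within the period, and on the stated maximum having been applied to the amounts given. The consequence is confined to a descriptive table. The primary analysis is on the mITT Population and does not use compliance, and no effect on per-protocol membership is shown. Severity: minor.

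**What to change.** Reconcile Section 9.2 with the maxima already stated in Sections 4 and 4.3. Suggested wording: the expected quantity is the daily amount or volume issued by the IWR system for the subject, multiplied by the number of days at that amount and summed over dispensing periods. The issued amount should already carry the body weight used, the applicable documented maximum and the mid-study recalculation; confirm this against the IWR specification. Using issued volume also gives placebo subjects a usable denominator, which a mg/kg/day dosage cannot.

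The cost is one sentence in the SAP and a small change to the compliance program. No dose, population or efficacy analysis changes. If the bottle-weight tables have already been produced, check which denominator was programmed and either rerun them or add a footnote.

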6.6.2. Definitions

First Dose Date: First Dose Date of Investigational Drug: If the first diary date on the day after randomization indicates that investigational drug was taken on this day, then the first dose date will be the date after randomization (Study Day 1). In all other situations where it is known that the subject took at least one dose of medication, the first dose date will be assumed to be 1 day after the date of randomization.

Study Day: Study day will be calculated relative to the First Dose Date in the Titration Period. For any date on or after the date of first dose, study day will be calculated as assessment date - first dose date + 1. For any date prior to the date of first dose, study day will be calculated as assessment date - first dose date. There will be no Study Day 0.

Baseline Value: For non-seizure frequency assessments, the Part 1 baseline value will be the last non-missing assessment collected on or prior to the first date of dosing in Part 1. Unscheduled assessments prior to First Dose Date will be considered for selection of the baseline value. Baseline values for seizure frequency endpoints will be

Event Start and End Dates

Inssing start and end date will be imputed conservatively, i.e. missing values will be imputed in such a way that the duration of the AE is considered with the longest possible duration and such that, whenever the AE may potentially start after first date of study medication, the AE will be handled as a treatment-emergent adverse event (TEAE).

The missing Start date and End date of an AE will be imputed for the calculating treatment emergent status and assigning events of lefinitions given in the following table.

Adverse event | Partial | Missing | Mi

	Adverse event
Partial /Missing Start date	Missing day - If Adverse event day is missing but month and year is present then Impute the 1st of the month unless month is same as month of first dose of study drug in Part 1 then impute first dose date in Part 1. Missing day and month - If adverse event day and month are both missing but year is present then impute 1st January unless year is the same as first dose date in Part 1 then impute first dose date in Part 1. Completely missing - impute first dose date in Part 1 unless the end date suggests it could have started prior to this in which case impute

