9.3.1. Overview of Adverse Events

The number and percent of subjects with at least one of the following events will be summarized in an overall summary table:

- TEAE
- Related TEAE
- Serious TEAE

- Related serious TEAE
- Severe TEAEs
- Severe related TEAE
- Adverse events of special interest
- TEAEs leading to premature discontinuation of study treatment
- TEAEs leading to premature discontinuation from the study
- Death

authorization areof. This overall summary table will be presented for the full Part 1 period, Titration Period Maintenance Period, Titration + Maintenance Period, and Taper/Transition Period.

For the full Part 1 period, Titration Period, and Titration + Maintenance Period, the denominator for the calculation of percentage will be the number of subjects in the SAF for the treatment group. For the Maintenance Period, the denominator for the calculation of the percentage will be the number of subjects for the treatment group with Part 1 last dose strictly greater than the date of Visit 6. For the Taper/Transition Period, the denominator for the calculation of the percentage will be the number of subjects for the treatment group with last dose strictly greater than the date of Visit 12.

9.3.2. **Treatment Emergent Adverse Events**

The following summaries will display the number and percentage of subjects with an adverse event as well as the corresponding number of events by system organ class (SOC) and preferred term (sorted alphabetically):

- All TEAEs
- Serious TEAEs
- TEAEs by Maximum Severity
- Study Drug Related TEAEs
- All TEAEs leading to premature discontinuation from the study

These summaries will present the TEAEs presented for the full Part 1 period, Titration Period, Maintenance Period, Titration + Maintenance Period, and Taper/Transition Period.

Summaries of TEAEs and Study Drug Related TEAEs will be summarized for the following subgroups:

- Age: 2- <6 years, 6-<12 years, 12 <18, $\ge 18 35$ years.
- Sex

- Concomitant usage of most commonly used concomitant Anti-epileptic medications (e.g. Valproate or other medications of interest; to be determined)
- # of con AEDs

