Table	14.3.1.2.2.2	Treatment-Emergent Adverse Events in Part 1 by MedDRA System Organ Class and Preferred Term by Age Group (Cohort B - Japan) - Safety Population	
Table	14.3.1.2.3.1	Treatment-Emergent Adverse Events in Part 1 by MedDRA System Organ Class and Preferred Term by Sex (Cohort A North America, Europe, Australia)- Safety Population	
Table	14.3.1.2.3.2	Treatment-Emergent Adverse Events in Part 1 by MedDRA System Organ Class and Preferred Term by Sex (Cohort B - Japan)- Safety Population	
Table	14.3.1.2.4.1	Treatment-Emergent Adverse Events in Part 1 by MedDRA System Organ Class and Preferred Term by Most Commonly Used Antiepileptic Medications (Cohort A - North America, Europe, Australia)- Safety Population	
Table	14.3.(.2,4.2	Treatment-Emergent Adverse Events in Part 1 by MedDRA System Organ Class and Preferred Term by Most Commonly Used Antiepileptic Medications (Cohort B - Japan)- Safety Population	
Table	14.3.1.2.5.1	Treatment-Emergent Adverse Events in Part 1 by MedDRA System Organ Class and Preferred Term by Number of Antiepileptic Medications Used (Cohort A - North America, Europe, Australia)- Safety Population	
Table	14.3.1.2.5.2	Treatment-Emergent Adverse Events in Part 1 by MedDRA System Organ Class and Preferred Term by Number of Antiepileptic Medications Used (Cohort B - Japan)- Safety Population	

versi	on 2.0	Syneos Health #1009529A	
Table	14.3.1.3.1.1	TEAEs Leading to Study Discontinuation in Part 1 by MedDRA System Organ Class and Preferred Term (Cohort A - North America, Europe, Australia)- Safety Population	:12tion
Table	14.3.1.3.1.2	TEAEs Leading to Study Discontinuation in Part 1 by MedDRA System Organ Class and Preferred Term (Cohort B - Japan) - Safety Population	ilou
Table	14.3.1.4.1.1	Serious TEAEs in Part 1 by MedDRA System Organ Class and Preferred Term (Cohort A - North America, Europe, Australia) - Safety Population	eo's.
Table	14.3.1.4.1.2	Serious TEAEs in Part 1 by MedDRA System Organ Class and Preferred Term (Cohort B - Japan) - Safety Population	
Table	14.3.1.5.1.1	Treatment Related TEAEs in Part 1 by MedDRA System Organ Class and Preferred Term (Cohort A - North America, Europe, Australia)- Safety Population	
Table	14.3.1.5.1.2	Treatment Related TEAEs in Part 1 by MedDRA System Organ Class and Preferred Term (Cohort B - Japan)- Safety Population	

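### Treatment-emergent status is set by start date alone, so a baseline-onset AE that worsens, turns serious or stops treatment after first dose is left out of the TEAE summaries unless it is re-entered as a new record

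*SAP*

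**What the plan says.** Section 9.3 defines a Part 1 TEAE as "any AE that based on start date information occurs after the first intake of study treatment in Part 1", with an upper limit at the first dose in Part 2. It then states the complement: "AEs occurring after enrollment and prior to the first administration of study treatment in Part 1 are defined as non-treatment emergent AEs (non-TEAEs". It assigns each TEAE to Titration, Maintenance or Transition/Taper by onset date.

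Collection starts earlier than the TEAE window: "the period of observation for adverse events extends from the time the subject gives informed consent". Section 4 gives the length of the pre-dose stretch: "Part 1 consists of a 4-week baseline, 2-week titration, 12-week maintenance".

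The overview in Section 9.3.1 counts subjects with serious, severe and related TEAEs and, among other rows, "TEAEs leading to premature discontinuation of study treatment". The SOC/PT summaries in Section 9.3.2 cover all, serious, maximum-severity and related TEAEs and "All TEAEs leading to premature discontinuation from the study". The table index in Section 14 follows the same restriction, for example "Serious TEAEs in Part 1 by MedDRA System Organ Class and Preferred Term".

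Section 9.3.2 also specifies listings for all enrolled subjects of all AEs (with TEAEs identified), serious AEs, AEs leading to study discontinuation, and deaths. These are not limited to TEAEs.

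**The concern.** Worsening of a pre-existing event on treatment is one of the things a TEAE table is meant to show. The definition here looks only at when an event began, not at what happened to it after dosing. A subject could have a mild event in baseline that becomes severe or serious, or causes treatment to be stopped, during titration or maintenance, and the corresponding summary row would not move.

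This matters more because Section 9.3.2 rules out inferential comparison of AEs, so the descriptive counts by arm carry the comparative safety message.

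It also sits oddly with the rest of the plan, which resolves doubt conservatively. An AE with missing severity is treated as severe, a TEAE with missing relationship is treated as related, and under Section 6.6.2 an AE with an uncertain start date is treated as emergent: "whenever the AE may potentially start after first date of study medication, the AE will be handled as a treatment-emergent adverse event". An event known to have deteriorated on treatment gets no such treatment.

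**Working it through.** No arithmetic applies: the SAP gives no AE rates, and the point turns on a definition. The check is to follow one type of event through the rules.

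Take an AE with a complete start date in baseline, say Study Day -10, mild at onset. After first intake it becomes severe, is then judged serious, and study treatment is stopped because of it.

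1. **Is it recorded?** Yes. Section 9.3 opens AE observation at informed consent. Section 6.7 sets baseline as the 28 days before Study Day 1, so Day -10 falls inside it.
2. **Does the date-imputation rule in Section 6.6.2 make it emergent?** No. That rule acts on missing or partial dates. A complete baseline date is left as it is.
3. **Is it a TEAE under Section 9.3?** No, if it keeps its start date. The onset is before first intake, and the complementary sentence places it among the non-TEAEs. Neither sentence has an exception for worsening, seriousness or discontinuation.
4. **Which summaries omit it?** The TEAE, serious, severe, related and discontinuation rows in Section 9.3.1; all five SOC/PT summaries in Section 9.3.2; and the matching tables in Section 14. The table of events in at least 5% of subjects and the AESI tables are also titled treatment-emergent in the index. The index has no summary table of non-TEAEs.
5. **Does the 2021 addendum change this?** No. It adds AE tables, all titled treatment-emergent, and leaves the definition alone.
6. **Where is it still visible?** In the listings of all AEs, SAEs and, if the subject leaves the study, discontinuations due to AE (Sections 9.3.2 and 14). For a subject who leaves the study, also in the disposition table by arm and reason (Section 7.1). The death and AESI rows of the Section 9.3.1 overview do not carry the word TEAE, so a death following such an event could be counted there.
7. **What if the site enters the worsening as a new AE with a post-dose start date?** Then step 3 gives yes, and the event is in every relevant table. The SAP contains no statement that this is done.

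The size would be the product of four quantities: subjects per arm; the share with a baseline AE still ongoing at first dose; the share of those whose event worsens, turns serious or stops treatment; and the share of such changes not entered as new records. The SAP gives an expected value only for the first.

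**The case against.** The strongest objection is that whether a worsened event keeps its old start date or becomes a new record is an AE-collection rule, normally found in the protocol or the eCRF guide, and neither is shown. If new records are the convention, the start-date rule captures the worsening and nothing is lost. This stands as a condition on the point. It does not remove it, because the TEAE definition belongs to the SAP, is stated there in full, and neither mentions nor depends on such a convention.

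A reader might infer that these events disappear from the report. The SAP does not support that. They remain in the listings, and study withdrawals for adverse events are counted by arm in disposition. Some on-treatment deterioration is also summarised outside AE coding: weight and BMI changes (Section 9.6), laboratory shifts from baseline (9.10), C-SSRS (9.11) and status epilepticus (8.4.6).

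A reader might also take Sections 9.4 and 9.5 as a second gap, since only new examination findings after first dose become AEs. But the same sections summarise subjects with clinically significant findings at each visit in T+M, with no restriction to new ones.

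These outputs do not replace the missing counts. Disposition covers leaving the study, which is not the same as stopping study treatment, and gives no preferred term, severity or seriousness. Listings do not give rates by arm.

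**Conclusion.** The point holds, conditionally. As written, the definition excludes from the TEAE, serious, severe, related and discontinuation summaries any baseline-onset AE that deteriorates after first intake and keeps its original start date. It does not exclude it from the listings or, for study withdrawals, from the disposition table.

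The size cannot be derived from the SAP. A reader might be tempted to estimate subjects lost per arm from assumed baseline AE and worsening rates. Such a figure would have no support in the document, would have to leave out events that resolved before dosing, and would have to keep events and subjects apart: Section 9.3.1 counts subjects with at least one event, so a subject with any other TEAE stays in the any-TEAE row and only the specific preferred-term, severity, serious or discontinuation entry is affected. Nor does the SAP show that the active arms would lose more than placebo. The rule applies equally to all arms, and the loss would differ only to the extent that worsening does.

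The conclusion rests on one assumption, that worsening is not entered as a new AE record. The matter concerns the completeness of the safety summaries and has no bearing on the primary efficacy inference. It is worth correcting because the rule is explicit and the change is small.

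**What to change.** In Section 9.3, define a Part 1 TEAE as an AE with onset after the first Part 1 intake, or an AE with earlier onset that after that intake increases in severity, becomes serious, or leads to discontinuation of study treatment. Keep the existing upper limit at the first Part 2 dose.

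Add a dating rule. Section 9.3 assigns events to periods by onset and Section 9.3.2 reports time to onset, so an earlier-onset TEAE would otherwise have no period and a negative time to onset. Assign such events to a period, and compute time to onset, from the date of worsening, of becoming serious, or of the action taken.

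If severity changes are not dated in the database, apply the rule at least to AEs whose recorded action is discontinuation of study treatment and to those with a recorded post-dose date of becoming serious. If the data-entry convention already requires a new record for worsening, state that in Section 9.3 and refer to it.

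Cost: a few sentences, a change to the TEAE flag, and some added programming for the dates. TEAE counts would rise slightly in all arms.
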